Data will be reported quantitatively. All analyses will be performed from the intention-to-treat principle. Missing data on background variables will be dealt with by multiple imputation. Final data analysis will begin when the last participant in the multicentric RCT has completed the follow-up period. The primary endpoint, work absenteeism due to illness, will be reported as the total number of sick days with standard deviation. Total days of absenteeism will be analysed using a Bayesian negative binomial regression with a fixed effect for BCG, hospital, professional category, age, enrolment week and number of average workdays per week. The brm function from the R package "brms" will be used for fitting the negative binomial model. The effect will be reported as a relative risk with 95% confidence interval (CI). Please refer to section interim analysis for type-1 error control and power.

Similar regression models will be used for secondary endpoints. Cumulative incidence outcomes will primarily be analysed using Cox Proportional Hazard Regression.

Continuous baseline characteristics will be reported as means with the standard deviation or medians with the inter-quartile range, as appropriate. Categorical baseline characteristics will be reported as count and percentage. No statistical testing for baseline characteristics will be reported.

Please refer to the Data Analysis Plan for more details.

Interim analysis

Every month, an interim analysis will be conducted for each study site and of the combined dataset. Interim analyses will start after the 200th participant has been recruited across the two sites. The primary endpoint will be analysed as described above. The Bayesian model yields a posterior distribution of the relative risk (RR). The posterior probability of the superiority hypothesis ($RR < 1$) will be calculated. If during any of the interim analyses, the posterior probability of superiority is > 0.995 , a conclusion is reached, and the trial will be stopped.

Monthly, the following secondary endpoints will be reported from the sites: hospital admissions, and deaths.

IMPLEMENTATION

Inception

The study will begin with an inception meeting to be held in Cape Verde or virtually, depending on travel and quarantine recommendations at the time. Besides administrative issues, the meeting will address:

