Known allergy to (components of) BCG or serious adverse events to prior BCG administration; known previous, active or latent infection with *Mycobacterium tuberculosis* or other mycobacterial species, fever (>38 C) within past 24 hours; previous confirmed COVID-19 (positive test by PCR or antibody) until inception of COVID-19 vaccination of HCW; suspicion of active viral or bacterial infection, severely immunocompromised subjects, self-reported HIV infection (Guinea: HIV-rapid test), self-reported pregnancy; active solid or non-solid malignancy or lymphoma within the last two years; any other contraindications for live-attenuated vaccine administration, not having a telephone.

Randomization

All participants who give consent for participation and who fulfil the inclusion criteria will be randomly assigned to either placebo or BCG group with a 1:1 (treatment:placebo) allocation in varying block sizes of 4 or 6 per block within strata defined by gender (male/female) and occupational group (doctors/nurses/other).

Blinding

The BCG vaccine was administered by study physicians/nurses, who are not blinded but also not involved in the data collection. Participants and follow-up assistants will be blinded to the treatment allocation. In case of serious adverse events, the participant can be unblinded after consultation with the investigator or the vaccinating physician/nurse. When the study has ended, all participants will receive information about the intervention that they received.

Intervention

The intervention consists of the administration of an intradermal injection of a standard 0.1 ml adult dose of attenuated *Mycobacterium bovis* BCG (Bacillus Calmette-Guerin), Danish strain 1331, $2-8 \times 10^5$ CFU or the placebo comparator: intradermal standard 0.1 ml saline solution (NaCl 0.9%). Both BCG and saline solution will be injected in the skin over the upper deltoid muscle.

Outcomes

Primary outcome measure: Total numbers of days of unplanned absenteeism from work due to illness.

Secondary outcome measures: Days of unplanned absenteeism because of documented COVID-19 and cumulative incidence of hospital admissions due to illness (minus accidents).

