Data will be reported quantitatively. All analyses will be performed from the intention-to-treat principle. Missing data on background variables will be dealt with by multiple imputation. Final data analysis will begin when the last participant in the multicentric RCT has completed the follow-up period. The primary endpoint, work absenteeism due to illness, will be reported as the total number of sick days with standard deviation. Continuous baseline characteristics will be reported as means with the standard deviation or medians with the inter-quartile range, as appropriate. Categorical baseline characteristics will be reported as count and percentage. Statistical testing for baseline characteristics will be performed. Days of absenteeism will be analysed using a Bayesian negative binomial regression with a fixed effect for BCG, hospital, professional category, age, enrolment week and number of average workdays per week. Incidence data will be analysed in Cox proportional hazards models. Monthly, data on absenteeism by randomization group will be reported to the DSMB.

Trial registration

The trial is registered at clinicaltrials.gov. (<https://clinicaltrials.gov/ct2/show/NCT04641858>)

Funding

EDCTP is funding the run-in costs for the BCG-COVID-RCT, including trials in the respective countries and for training and management.

Study management, monitoring and quality control

The project is led by an International Steering Committee (ISC) consisting of PIs in each of the five countries involved: [name] (international coordinator), PI from Denmark; [name], PI from Guinea-Bissau; [name], PI from Portugal; [name], PI from Cape Verde; and [name], PI from Mozambique. The overall coordination is the responsibility of the Danish partner. The leader has extensive leadership experience from running a Center of Excellence in Denmark and the research group of the Bandim Health Project in Bissau for many years. The Bandim Health Project has a history of past collaboration with the Portuguese partner. The research group will hold teleconferences at least once a week with a formal pre-established agenda on training, enrollment, follow-up, losses to follow-up, staff turnover, vaccine logistics, quality control of data collection, data entry and database management, interim analysis, communication and dissemination activities, other risks. Decisions from each meeting are recorded by the coordinator.

2. Definitions

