Primarily a descriptive analysis will be performed of all information contained in the two study groups (BCG and placebo). All variables will be analysed, one by one, to know their distribution. Background factors will be summarised by counts (percentages), means (standard deviation) or medians (interquartile range) as appropriate. Proportions will be compared using the chi-square test - χ^2 test or Fisher's Exact test (categorical variable) or Student's t-test or Mann-Whitney test (quantitative variable) according to the distribution of variables. Statistical significance was set at the 5% level (two-tailed tests) and 95% confidence intervals (95%CI) for the estimates.

The endpoints variables (table 1) will be analyzed using univariate analysis (Logrank test) and Multivariate analysis (Cox Proportional Hazard Regression, or Cox Regression), stratified by the block randomization variables gender (male/female) and occupational group (doctors/ nurses/other) in addition to site. Covariates will be tested in the model univariate, and only those that were associated with the outcome at a significance level of at least 20% will be retained in a possible multivariate model. A significance level (p-value) of less than 0.05 and its respective confidence intervals (CI) will be used.

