For the univariate analysis to check the difference between the BCG versus Placebo groups we will use the Logrank test of significance by means of its p-value or confidence interval. For the univariate analysis to check the difference between the BCG versus Placebo groups we will use the Logrank test of significance by means of its p-value or confidence interval. In the multivariate analysis for the comparison of the two analyzed groups, we will use the Cox Proportional Hazard Regression, or Cox Regression. This allows us to obtain results adjusted for possible confounding variables. Cumulative incidence data will be analysed in Cox proportional hazards models. The Cox Model, which is semi-parametric, assumes that failure rates are proportional, that is, the risk of failure of the variables is constant over time. Survival analysis will allow us to correctly assess the rate at which events (outcomes) are occurring in the different groups in our study.

7. Demographics and other baseline characteristics

Baseline characteristics

Table 2 – Baseline characteristics of the participants

Variable	Type	BCG vaccine	Placebo	Statistical (P-value)
Age (years)	Quantitative	$\bar{X} \pm SD$ or Md (IQR)	$\bar{X} \pm SD$ or Md (IQR)	Student's t-test or Mann-Whitney test
Gender				
Female	Categorical	% (n/N)	% (n/N)	χ^2 test or Fisher's exact test (P-value)
Male		% (n/N)	% (n/N)	
Number adults (> 18 years) living in the household	Quantitative	$\bar{X} \pm SD$ or Md (IQR)	$\bar{X} \pm SD$ or Md (IQR)	Student's t-test or Mann-Whitney test
Adult living at home and also healthcare worker	Quantitative	$\bar{X} \pm SD$ or Md (IQR)	$\bar{X} \pm SD$ or Md (IQR)	Student's t-test or Mann-Whitney test
Number children (<18 years) living in the household	Quantitative	$\bar{X} \pm SD$ or Md (IQR)	$\bar{X} \pm SD$ or Md (IQR)	Student's t-test or Mann-Whitney test
Age of the youngest child living in the household (years)	Quantitative	$\bar{X} \pm SD$ or Md (IQR)	$\bar{X} \pm SD$ or Md (IQR)	Student's t-test or Mann-Whitney test
Animals living in the household				
Dogs	Categorical	% (n/N)	% (n/N)	χ^2 test or Fisher's exact test (P-value)
Cats		% (n/N)	% (n/N)	
Pigs		% (n/N)	% (n/N)	

Variable	Type	BCG vaccine	Placebo	Statistical (P-value)	
Birds		% (n/N)	% (n/N)		
Sheep		% (n/N)	% (n/N)		
Other		% (n/N)	% (n/N)		
Person living in the household diagnosed with COVID-19					
No	Categorical	% (n/N)	% (n/N)	χ^2 test or Fisher's exact test (P-value)	
Yes		% (n/N)	% (n/N)		
Occupation					

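### The SAP tests every baseline characteristic for a difference between arms, although the protocol says no such tests will be reported; about two of 37 would be significant by chance

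*SAP*

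**What the plan says.** The two documents describe baseline reporting in nearly the same terms (means or medians, counts and percentages) and then part.

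- Protocol, Data analysis: "No statistical testing for baseline characteristics will be reported". The section then refers the reader to the Data Analysis Plan for further detail.
- SAP, Statistical analysis: "Statistical testing for baseline characteristics will be performed".
- SAP Section 7, "Table 2 – Baseline characteristics of the participants": the last column is for p-values, and each variable has a t-test or Mann-Whitney test, or a chi-square or Fisher test.
- SAP 6.1 names the same tests straight after the summary of background factors and adds: "Statistical significance was set at the 5% level (two-tailed tests".

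Three rules govern adjustment:

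- The absenteeism model has a "fixed effect for BCG, hospital, professional category, age, enrolment week and number of average workdays per week". The same list stands in the protocol's Data analysis section and in SAP 6.4.
- The Poisson models for COVID-19 infection and death include the stratification variables (footnote to SAP Table 5).
- The Cox models are stratified by gender, occupational group and site. Other covariates stay if they are associated with the outcome at the 20% level in univariate analysis (SAP 6.1). SAP 6.4 says of the Cox model: "This allows us to obtain results adjusted for possible confounding variables". Neither section lists the candidates.

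**The concern.** An analyst cannot follow both documents. The protocol defers to the analysis plan for detail, so the SAP should elaborate the protocol's rule. Instead it reverses the rule without giving a reason.

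The reversed rule is also the weaker one. Participants are "randomly assigned to either placebo or BCG group with a 1:1 (treatment:placebo) allocation", and SAP 6.1 says that the allocation table was not available to the researchers. Under such a procedure the null hypothesis of a baseline test is true by design, so a small p-value can only be a chance finding. Gender and occupation are tested too, although allocation was blocked "within strata defined by gender (male/female) and occupational group (doctors/nurses/other" and they are balanced by construction.

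At stake is a published baseline table with a couple of significant rows that mean nothing and that readers may take for a flaw in the randomisation. A separate, smaller matter is that the Cox covariates are chosen from the data.

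**Working it through.** The documents give no number of baseline tests and no expected number of chance findings, so there is no stated figure to reproduce.

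**Inputs**
- Rows in SAP Table 2 that carry a test: 37, by count from age to number of smallpox scars.
- Stratification factors among them: 2 (gender, occupation).
- Rows made up of several items: animals (6), symptoms (10) and type of chronic disease (9), 25 items in all. Tested one by one, they give 37 - 3 + 25 = 59 tests.
- Level: 0.05, two-sided (SAP 6.1).

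**Formulas for m tests of true null hypotheses**
- Expected number with p < 0.05: m x 0.05. This does not require independence.
- Chance of at least one: 1 - 0.95^m. This does require independence.
- Chance of at least two: 1 - 0.95^m - m x 0.05 x 0.95^(m-1). This also requires independence.

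| Tests counted | m | Expected | At least one | At least two |
|---|---|---|---|---|
| All rows | 37 | 1.85 | 85% | 56% |
| Without the two strata | 35 | 1.75 | 83% | 53% |
| Items tested one by one | 59 | 2.95 | 95% | 80% |
| Items, without the strata | 57 | 2.85 | 95% | 79% |

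Under the protocol's rule m = 0, and so is the expected count.

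**Limits of these figures.** Several rows overlap or are nested: absence yes/no and days absent; hospitalisation yes/no and days; COVID-19 vaccine, type and dose; the BCG vaccination and scar rows. The percentages are therefore approximate. The expected count survives dependence, but it assumes that each test has a true size of 5%. Fisher's test, which SAP 6.4 itself calls conservative, would pull it down somewhat.

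**Where the baseline p-values go.** Set side by side, the three adjustment rules contain no step that takes a p-value from Table 2. The absenteeism list is fixed, the Poisson models use the strata, and the Cox screen looks at covariate against outcome, not covariate against arm.

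**The Cox screen.** A 20% screen passes one unrelated covariate in five. If the candidates were the 37 Table 2 rows (an assumption, since no list is given), 0.20 x 37 = 7.4 unrelated covariates would be expected to pass by chance.

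**The case against.** Four points can be made for the plan.

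- **Performing is not reporting.** The two sentences use different verbs and could both be obeyed if the tests were run and kept out of the report. The p-value column of Table 2 closes that route.
- **The tests could check the conduct of the randomisation.** The vaccinators are not blinded, so some check on allocation has a purpose. But the SAP gives the tests no such purpose and attaches no action to a significant result. With 37 unadjusted tests, one or more significant rows would be likely even if conduct were perfect.
- **The 85% overstates what is known.** This stands. It needs independence, and Table 2 visibly lacks it. Only the expected count of about two should be relied on.
- **Nothing depends on these p-values.** This also stands, and it limits the point. A reader might infer that chance imbalances will steer the adjusted treatment effect, because SAP 6.4 speaks of adjusting for possible confounders. The documents do not support that reading. The sentence describes what Cox regression can do and does not mention Table 2, and the selection rule actually stated, in SAP 6.1, concerns association with the outcome. Nor do the documents say that a significant row would be treated as evidence against the randomisation.

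**Conclusion.** The contradiction between protocol and SAP is certain, and the protocol's rule is the sound one. The SAP's rule would be expected to yield about two chance findings in the baseline table: 1.85 on the row count, with a range of 1.75 to 2.95 depending on whether the strata are counted and multi-item rows are split. This rests on a properly executed randomisation and on tests of nominal 5% size.

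The primary estimate is unaffected, because its covariates are fixed in advance. Open covariate choice is limited to the Cox analyses of secondary and other endpoints. There it comes from the 20% outcome screen and the missing candidate list, and removing the baseline tests would leave it in place. This assumes that the screen belongs to the incidence endpoints. SAP 6.1 refers to the Table 1 endpoints in general, but the Statistical analysis section, 6.4 and Table 4 place absenteeism in the Bayesian model.

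Severity: minor.

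**What to change.** 1. In the SAP's Statistical analysis section, delete the sentence that calls for baseline testing. In Section 7, delete the p-value column of Table 2. The summaries by arm stay, so no descriptive information is lost.
2. In SAP 6.1, state that the group-comparison tests do not apply to baseline variables. The same note is needed where 6.4 repeats those tests.
3. In SAP 6.1 and 6.4, replace the 20% screen and the reference to unlisted confounders with a pre-set list for the Cox models: gender, occupational group and site, plus any covariates already listed for the primary model. Both sections must be amended together. Restricting adjustment elsewhere while 6.1 keeps the screen would create a new contradiction.

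The cost is SAP wording only. The analysis becomes shorter, and no data collection or sample size changes.

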2.1. Treatment groups

Single-blind, parallel-group placebo-controlled adaptive multi-center trial, with block randomisation 1:1 to intradermal standard 0.1 ml dose of BCG vaccine or placebo (saline) including a total of 1050 HCW (BCG arm and placebo arm). The intervention will consist of the administration of an intradermal injection of a standard 0.1 ml adult dose of attenuated *Mycobacterium bovis* BCG (Bacillus Calmette-Guerin), Danish strain 1331, $2-8 \times 10^5$ CFU or the placebo comparator: intradermal standard 0.1 ml saline solution (NaCl 0.9%).

Both BCG and saline solution will be injected in the skin over the upper deltoid muscle. The BCG vaccine is being administered by healthcare professionals who are not blinded to the intervention administered, but who will also not be involved in data collection during follow-up. Participants, research assistants and analysts are blinded to the intervention received. In the event of serious adverse effects, the participant may be revealed the intervention they received, after consultation with the investigator or physician/nurse. When the study ends, all participants are informed about the intervention they received.

2.2. Analyzed populations

The clinical trial participants are 1,050 HCW (definition below) recruited from hospitals in two different African countries.

The Guinea-Bissau arm of the BCG-COVID-RCT study is conducted in Bissau, the country capital, by the Bandim Health Project (BHP). The team is led by [name]. Inclusions commenced in Guinea-Bissau on December 3rd, 2020, in the Hospital Nacional Simão Mendes. After concluding inclusions at Simão Mendes, inclusions were commenced at other hospitals and health centers.

In Mozambique, this study is being conducted at Manhiça District Hospital (MDH) and Mavalane General Hospital (MGH) by the Centro de Investigação em Saúde de Manhiça (CISM) through the team led by [name]. Manhiça District Hospital is located on the main National Road One, in the capital of the Manhiça district, Maputo Province, southern Mozambique. Manhiça is a rural area located approximately 80km away from the capital, Maputo city; has a total population close to two hundred thousand people. MDH is the referral hospital with more than 100 beds and absorbs the largest proportion of HCW within the district. MGH (260 beds) is located in the district of neighborhood of Mavalane, in Maputo city (Southern Mozambique). The MGH is part of the three general hospitals of the city of Maputo. The health

area of Mavalane is the largest in the city and serves an estimated population of 609.889 inhabitants, about 50% of the health population of the capital of nation capital.

2.3. Study definitions

- **Health Care Workers (HCW)** defined as a person who provides service and/or care to patients/users attending the health care facilities participating in the study, either directly (nurses, nursing assistants, physicians, and medical students), or indirectly as aides, lab technicians, cleaning staff, or even medical waste handlers.
- **SARS-CoV-2 ("Severe Acute Respiratory Syndrome Coronavirus 2")** defined as a virus associated with or responsible for COVID-19.
- **COVID-19** is a disease caused by the coronavirus (a large family of viruses common in many different animal species, including camels, cattle, cats and bats), called SARS-CoV-2, which has a clinical spectrum ranging from asymptomatic to severe infections. The symptoms of COVID-19 can range from a cold to a Gripal Syndrome-SG (presence of an acute respiratory condition characterized by at least two of the following symptoms: febrile feeling or fever associated with sore throat, headache, cough, runny nose) to severe pneumonia.
- **BCG (Bacillus Calmette-Guérin)** vaccine is composed of Bacillus Calmette & Guérin, obtained by attenuating *Mycobacterium bovis*, one of the bacteria that transmit tuberculosis. This vaccine prevents tuberculosis, an infectious disease that most commonly attacks the lungs, but can also cause infections in the bones, kidneys and meninges (the membranes that surround the brain).
- **Placebo** is a simulated drug that does not contain any chemical or medicinal substance and can only influence the individual taking it psychologically. In a clinical trial, a placebo is a pharmaceutical form without any activity, taken by the patients in the control group, and identical in appearance to the pharmacologically active pharmaceutical form(s) taken by the subjects in the other treatment group(s) of the trial.
- **Clinical Trial (Clinical Study or Clinical Research)** is a method of scientific investigation applied to human beings in order to prove the efficacy of treatments or drugs, the probable benefits and adverse events, as well as to make possible the offer of treatments not yet applied in clinical practice.
- **Randomized ("chosen at random")**: This is any randomization procedure (in our study we will use a computer program - REDCap - for the randomization of participants. In this way, all subjects participating in the trial will have strictly the same probability of receiving the BCG vaccine or the one corresponding to the study control (placebo).

- **Absenteeism** is referred to as the total number of absences (in days) of the health worker care due mainly to some illness.

3. Sample size

Our sample size was defined based on the calculations made by the Dutch group which computed in 1000 the minimum sample size. We decided include 350 participants per site(Cape Verde, Guinea Bissau and Mozambique) which adds 1050 participants. This participants number is near enough to show significance for the primary outcome - expected absenteeism reduction from 5% to 4%.

Based on current experience, the investigators consider that this a feasible sample size, which well balances burden of participants against public interest. As this is an adaptive study, the final follow-up duration is subject to the percentage of absenteeism during the study period, variation in absenteeism between participants, and the true effect of BCG vaccine.

4. Recruitment and follow-up

The RCT involves healthy, volunteer human participants able to give informed consent to participate in an interventional trial consisting in the intradermal administration of BCG vaccine standard dose or placebo (saline).

The participants in this research are HCW. Prior to the initiation of the trial, the hospital director will inform the department heads about the trial. For recruitment we performed a rapid test (POC test) for antibodies against SARS-CoV2 using the COVID-19 IgG/IgM CTK OnSite COVID-19 IgG/IgM Rapid Test (<https://ctkbiotech.com/covid-19/>). The test is performed by collecting a drop of blood (maximum 0.4 ml of blood) from a fingerstick. The participant was informed about the POC test result and the interpretation of what it means to having or not having IgM and/or IgG antibodies. If the result is positive for IgM antibodies, we recommend that the HCP be tested for SARS-CoV2 with a swab in the throat (PCR test), according to the recommendations of local health authorities. The BCG vaccine was administered by people trained to administer vaccines by the intradermal technique. The injection site should be clean and dry. The vaccine was injected intradermally on the outer side of the upper arm, corresponding to the area of the distal insertion of the deltoid muscle (about one-third down the upper arm).

Follow-up will last for 6 months (182 days). Every second week, participants will be contacted over telephone and interviewed for symptoms and absenteeism from work. By the end of follow-up,

participants will be invited for another POC test for COVID-19 serology. The study relies on bi-weekly telephone follow-up. Participants have indicated whether they prefer to be contacted during the morning, the afternoon or at any time during the day. The responsible assistant conducts the telephone follow-up every day and introduces the data on absenteeism and causes, COVID-19 testing (if done) and their results on the WiFi-connected tablet during the interview. This data can be supplemented by daily workplace presence registry information (where present). An explicit permission for this procedure will be requested from the participant during informed consent procedures at enrolment.

5. Endpoint variables

The endpoint variables are described in Table 1

Table 1 – Definition of end-points variables

Variable	Definition	Type	Scale	Domain
Absenteeism	Refers to the total number of days absent from work due to illness	Quantitative	Numeric	In days
Absenteeism for COVID-19	Refers to the number of days absent from work due to COVID-19	Quantitative	Numeric	In days
Absenteeism besides COVID-19	Refers to the number of days absent from work due to illness besides COVID-19	Quantitative	Numeric	In days
Absenteeism for infections	Refers to the number of days (unplanned) absent from work due to infections	Quantitative	Numeric	In days
Absenteeism for respiratory infections	Refers to the number of days (unplanned) absent from work due to respiratory infections	Quantitative	Numeric	In days
COVID-19 infection	Describes if the participant is positive for SARS-CoV2 or has had COVID-19	Qualitative	Nominal	No Yes
Death	Whether the participant died during follow-up	Qualitative	Nominal	No Yes
Cumulative incidence of infectious disease episodes	Cumulative incidence of infectious disease episodes	Quantitative	Numeric	Episodes
Cumulative incidence of respiratory infectious disease episodes	Cumulative incidence of respiratory infectious disease episodes	Quantitative	Numeric	Episodes
Cumulative incidence of hospital admissions	Cumulative incidence of hospital admissions	Quantitative	Numeric	Admissions
Cumulative incidence of infectious disease hospital admissions	Cumulative incidence of infectious hospital admissions	Quantitative	Numeric	Admissions

Variable	Definition	Type	Scale	Domain
Cumulative incidence of respiratory infectious hospital admissions	Cumulative incidence of respiratory infectious hospital admissions	Quantitative	Numeric	Admissions
Cumulative incidence of hospital admissions due to documented COVID-19	Cumulative incidence of hospital admissions due to documented COVID-19	Quantitative	Numeric	Admissions
Cumulative incidence all-cause and infectious intensive care admission	Cumulative incidence all-cause and infectious intensive care admission	Quantitative	Numeric	Nights
Cumulative incidence of intensive care admission due to documented COVID-19 infection	Cumulative incidence all-cause and infectious intensive care admission	Quantitative	Numeric	Nights

6. General Statistical considerations

